In this study, we will enroll female pediatric emergency department (ED) patients presenting with a diagnosis of abdominal pain who may have a transabdominal pelvic ultrasound ordered by their treating physician (or nurse practitioner). In order to maximize the visualization of organs deep within the pelvis such as the ovaries and uterus, the patient's bladder must be full. The current practice at our institution, as well as numerous others, is to have a bladder catheter placed immediately when a transabdominal pelvic ultrasound is ordered, and then to fill the bladder in a retrograde manner in order to provide enhanced visualization of the pelvic structures. The process of inserting a bladder catheter into a pediatric patient is an invasive procedure which can be traumatic and painful to the patient. Additionally, if the patient's bladder is already full, this procedure may be unnecessary.

In this study, a point-of-care bladder ultrasound will be performed, upon enrollment of a patient by a study bedside sonographer (our pediatric emergency department nurse practitioners), to assess degree of bladder fullness. This measurement will then be repeated serially while the patient is receiving hydration and the ultrasound will be performed when the bladder is full. We hypothesize that this work flow will result in an equivalent time to transabdominal pelvic ultrasound completion and will reduce the number of potentially traumatic and painful, invasive urethral bladder catheterizations.

b. Describe how outcomes will be measured for this protocol. The primary outcome variable will be time to completed pelvic ultrasound, described as time from transabdominal pelvic ultrasound order placed to time of transabdominal pelvic ultrasound image completion.

Secondary outcomes include: proportion of urethral bladder catheterizations and patient's pain level with the process of point-of-care bladder ultrasound vs. bladder catheterization, as measured using Visual Numerical Rating Scale (VNRS) (see attached).

15. Background - in nontechnical, lay language

Summarize in 2-3 paragraphs past experimental and/or clinical findings leading to the design of this protocol. Include any relevant past or current research by the PI. For drug and device studies, summarize the previous results (i.e., Phase I/II or III studies).

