Published literature identifies that bladder volume can be accurately measured by point-of-care ultrasound, in qualitative and quantitative ways. Because accepted practice is to perform an invasive urethral catheterization into the bladder of pre- or adolescent females presenting with abdominal pain, when there is a concern for ovarian torsion or other ovarian/uterine pathology, the knowledge that non-invasive methods can predict visualization success, is an important one.

Dessie, et al. in Annals of Emergency Medicine, 2018, showed that not only could pelvic anatomy be well-visualized, but no incomplete pelvic ultrasounds occurred in patients who received their pelvic ultrasound based on point-of-care ultrasound for bladder volume, using a qualitative measure. This study also showed that the procedure could be readily taught and expertise in evaluating qualitative measurements of bladder volume could be reliably assessed after undergoing such brief training by individuals—in their case physicians or research assistants—who were not ultrasonographers.

Our study hypothesizes that similarly reliable results will be able to be obtained by CRNPs currently working in our pediatric ED, without adverse delays or detrimental outcomes in patient care. No such studies have looked at using this group of personnel to perform this goal-directed task to expedite diagnostic workup and avoid an invasive urethral bladder catheterization.

16. Participants (Screening and Selection)

a. How many participants are to be enrolled at UAB (if other sites relying on UAB IRB, list the number for each site)? 0

Children's of Alabama: 48

b. Describe the characteristics of anticipated or planned participants (if multiple groups, repeat list for each group).

Sex: **Female**

Race/Ethnicity: **All**

Age: **8-18**

Health status: **Participants will be females visiting the ED for abdominal, vaginal, or possible genitourinary-related complaints, which may include abdominal pain, vaginal discharge, pelvic bleeding, flank pain, or vomiting, and for which treating physicians/nurse practitioners have a concern for pelvic pathology, such as ovarian torsion, ovarian cysts, or other ovarian or uterine pathology.**

c. From what population(s) will the participants be derived? **Participants will consist of patients of the Department of Pediatric Emergency Medicine.**

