- a. Describe the procedures for all aspects of your protocol. Tell us what you are doing.

This study enrolls patients presenting to the pediatric ED for clinical complaints including, but not limited to, abdominal or pelvic pain, and for whom the treating physician/nurse practitioner anticipates ordering a transabdominal pelvic/ovarian torsion ultrasound.

Once it has been determined that the participant is eligible, and has provided written informed consent (or legal guardian), or assent (when appropriate), the patient will be randomized into the control or the treatment group. The control group will undergo the standard care where bladder catheterization and timing of imaging is at the treatment team's discretion.

In the intervention group, a study member who has completed asynchronous didactic and hands-on training in bladder ultrasound (see attached summary of US education) will perform a point-of-care bladder ultrasound for qualitative assessment of bladder fullness, using a SonoSite Exporte or SonoSite M-Turbo ultrasound machine. The exam will be performed during a time that does not interfere with the patient's care. This ultrasound will be obtained immediately upon enrollment and serially at 30-minute intervals until the bladder is determined to be full, either by a qualitative ultrasound bladder measurement (attached) OR by patient's sensation of bladder fullness (Bladder Fullness Scale, attached). Bladder Fullness Scale is a 4-point scale which is adopted from a urology bladder sensation measurement tool and has been used in previous, similar research.

If the bladder is not full by this qualitative assessment, the patient will receive additional hydration during the interval between repeated ultrasound examinations. This hydration will be provided by either an oral or intravenous route. The decision on administration of intravenous fluids will be made by the treating physician. Repeated point-of-care ultrasounds to assess bladder fullness will be attained at 30-min increments, or when a patient has the sensation of maximal fullness.

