Time to successful transabdominal pelvic ultrasound will be recorded. Bladder ultrasound images will be stored securely and reviewed by blinded ultrasound fellowship-trained or RDMS-certified attending emergency/pediatric emergency physicians to determine inter-rater reliability of the bedside ultrasound interpretation as well as for quality assurance. Such review will be conducted on a weekly or bi-weekly basis. A kappa of 0.6 to be considered excellent correlation.

At the conclusion of the intervention, the patient (or guardian, based on age), will be provided a survey regarding their satisfaction of the interventions, length of stay, and comfort level.

The following information will be recorded from the participant’s medical record:

- Volume of PO or IVF consumed
- Time of order of transabdominal pelvic ultrasound
- Time of completion of transabdominal pelvic ultrasound (as determined by time stamped on radiology report)
- Total ED length of stay, in minutes
- Door to MD/NP time, in minutes
- Outcome/condition at discharge
- MRN
- Visit Date
- Any adverse outcomes—complications with foley, severe pain, etc.
- Discharge diagnosis
- Patient weight (in kg)
- Patient age (in months/years)
- Race

b. What is the probable length of time required for the entire protocol (i.e., recruitment through data analysis to study closure)? **2 years**

c. What is the total amount of time each participant will be involved? Each participant’s time involved will vary, but is limited to the hospital length of stay. Interaction with each participant will last the amount of time needed to perform the consent process and the exam.

d. If different phases are involved, what is the duration of each phase in which the participants will be involved? If no phases are involved, enter “None.” **None**

e. List the procedures, the length of time the procedure takes, the total # of times the procedure is performed, and indicate whether each is performed solely for research or would already be performed for treatment or diagnostic purposes (routine care) for the population.

-Insert additional table rows as needed.

-If procedure is sometimes research and sometimes routine care, include on separate lines with number of times as each.

Procedure	Length of Time Required of Participants	Total # of Times the Procedure is Performed	Research (Res) –OR- Routine Care

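### The procedural-pain outcome has no pre-procedure VNRS score and no common rating time, in patients enrolled largely because they are already in pain

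*Protocol*

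**What the plan says.** **Outcome.** Item 14.b lists as a secondary outcome the patient's "pain level with the process of point-of-care bladder ultrasound vs. bladder catheterization, as measured using Visual Numerical Rating Scale (VNRS"), with the form said to be attached. It gives no time of rating and no baseline.

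**Population.** Item 14.a describes "female pediatric emergency department (ED) patients presenting with a diagnosis of abdominal pain". Item 17.a describes "clinical complaints including, but not limited to, abdominal or pelvic pain". The health-status entry in 16.b lists "abdominal pain, vaginal discharge, pelvic bleeding, flank pain, or vomiting". Pain is therefore the main reason for enrolment, but not the only one.

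**Procedures.** Item 17.a describes the bedside scans, their 30-minute spacing, the Bladder Fullness Scale and the hydration between scans. It mentions no pain rating before, during or just after a scan or a catheterization. It does schedule one survey: "At the conclusion of the intervention, the patient (or guardian, based on age), will be provided a survey regarding their satisfaction", which also covers length of stay and comfort level. The list of items to be taken from the medical record includes severe pain as an adverse outcome, but no pain score and no analgesia.

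**Arms.** Item 16.e plans 24 patients per arm. Item 17.a leaves catheterization in controls to the treating team, and item 19.c.iii allows treatment-arm patients to be catheterized later.

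**The concern.** The outcome is meant to capture pain caused by preparing the bladder. A patient who arrives with abdominal or flank pain may report some of that pain when asked about the procedure, and the presenting pain can change during the visit. Without a score taken beforehand, the two cannot be separated, and an imbalance in presenting pain between two arms of 24 can be neither seen nor adjusted for.

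The unstated rating time adds to this. If controls rate soon after a catheter and treatment patients rate after several scans, or the reverse, elapsed time and any analgesia become part of the contrast.

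Reducing painful catheterization is a main part of the rationale in 14.a, so the pain comparison will be read closely. A statistical analysis plan can choose the model, but it cannot supply a baseline that was never collected.

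**Working it through.** The protocol gives no SD, effect size or power for the pain outcome, so there is no stated figure to reproduce. What follows is an illustration.

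**Inputs.** From item 16.e: n = 24 per arm. Assumed: VNRS SD 2.5 points (range 2 to 3), and correlation r between the pre- and post-procedure scores of 0.3, 0.5 or 0.7.

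**Without a baseline score**
- SE of the difference = SD × √(2/n) = 2.5 × √(2/24) = 0.722.
- 95% CI half-width = t(46 df) × SE = 2.013 × 0.722 = 1.45 points.

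**With baseline adjustment.** The half-width is multiplied by √(1 − r²):

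| r | √(1 − r²) | SD 2 | SD 2.5 | SD 3 |
|---|---|---|---|---|
| none | 1 | 1.16 | 1.45 | 1.74 |
| 0.3 | 0.954 | 1.11 | 1.39 | 1.66 |
| 0.5 | 0.866 | 1.01 | 1.26 | 1.51 |
| 0.7 | 0.714 | 0.83 | 1.04 | 1.24 |

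**Detectable difference.** At 80% power and two-sided 5%, it is (1.960 + 0.842) × 0.722 × √(1 − r²). With SD 2.5 this is 2.02 points without a baseline, and 1.93, 1.75 or 1.44 at r = 0.3, 0.5 or 0.7. Power for an assumed 2-point difference is 79% without a baseline, and 83%, 89% or 97% with one.

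**Chance imbalance.** If presenting pain itself has SD 2.5, the arms' mean presenting pain will differ by chance within ±1.96 × 0.722 = ±1.41 points in 95% of trials. This is not an addition to the half-width of 1.45. The interval without a baseline already allows for it; a baseline score lets part of it be removed.

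**Where bias could enter**
- *Rating time.* Item 17.a spaces scans 30 minutes apart and the procedure table in 17.e allows at most 5, so the last scan could fall 4 × 30 = 120 minutes after the first. Item 19.c.i describes standard care as immediate catheter placement. If each rating follows its own procedure, elapsed time could differ by arm.
- *Procedure received.* The outcome in 14.b is worded as scan against catheterization. Controls need not be catheterized and treatment patients may be, so a comparison by procedure is not the randomized comparison.

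**The case against.** **The VNRS is not shown to be a late or guardian-reported score.** A reader might infer from 17.a that pain is rated once, at the end, possibly by a guardian. The document does not say so. The end timing and the guardian option are stated only for the satisfaction and comfort survey; nothing makes the VNRS part of it, and 14.b already assigns the pain rating to the patient. The attached form might even set a rating time. This objection stands: what can be said is that the visible text fixes no rating time and no pre-procedure score. The absence of a pain score from the medical-record list proves little, since the VNRS need not come from that record.

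**Randomization balances presenting pain.** A reader might infer that presenting pain biases the comparison whatever the analysis. Between randomized arms it is balanced in expectation, so that reading fails. Unequal rating times are possible but not stated: 14.a hypothesizes equal time to ultrasound, scanning stops once the bladder is full, and control timing is discretionary.

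**The outcome already asks about the process.** A rating that asks clearly about the procedure may correlate only weakly with presenting pain, and adjustment then gains little: at r = 0.2 the half-width is 1.453 × 0.980 = 1.42 against 1.45. That is fair. The gain depends on a correlation the protocol does not give.

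**It is a secondary outcome.** This is also true, and it limits the weight of the point. It does not alter the fact that a missing baseline cannot be repaired afterwards.

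**Conclusion.** The point holds as a gap in data collection. The protocol text sets neither a pre-procedure VNRS nor a common rating time for a procedural-pain outcome in patients who are largely in pain already.

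Compared by randomized arm with equal timing, the cost is precision. Under the assumed SD of 2.5, the interval is 1.45 points either side, where a baseline score would give about 1.39 to 1.04 for r between 0.3 and 0.7. Systematic bias is conditional on unequal rating times or a comparison by procedure received; the visible text excludes neither and establishes neither. The SD and the correlation are assumptions, and the unseen VNRS form could settle the rating time. The protocol should be changed on this point, but the primary outcome does not depend on it.

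**What to change.** In 14.b and 17.a:

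1. Have the patient give a VNRS at randomization in both arms.
2. Have the patient give a second VNRS under one common rule: right after the bladder-preparation step actually completed, meaning the last bedside scan or the catheterization, whichever is later. For controls who have neither, take it just before the pelvic ultrasound. Ask about pain from that step.
3. Compare the second score by randomized arm, adjusted for the score at randomization.
4. Keep any guardian-answered survey separate from the pain outcome.

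The rule covers controls who are not catheterized and treatment patients who are catheterized later. It fixes the event that triggers the rating, not the clock time since randomization, which may still differ by arm. Recording the time of each rating and any analgesia given would make such a difference visible.

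The cost is one extra brief rating per patient, a small burden on bedside staff, and wording changes to two items. No extra patients are needed.

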Describe your ability to obtain access to the proposed population that will allow recruitment of the necessary number of participants: **This will be a convenience sample, identified based on treating physician's suspicion that a transabdominal Pelvic Ultrasound/Ovarian Torsion Ultrasound (Order-set) will be placed and for whom arrival to the ED is between the hours of 0700-2300 on Mondays-Fridays, as this correlates with the times that sonographers are in-house, and hence real-time attainment, of transabdominal pelvic ultrasounds is achievable.**

d. Describe the inclusion/exclusion criteria:

Inclusion Criteria:

- Age 8yr-18yrs
- Female
- Likely to have order placed for transabdominal pelvic ultrasound/ovarian ultrasound

- No history of pelvic or bladder reconstructive surgery

Exclusion Criteria:

- Pregnancy (known)
- Critically ill patients
- Patients with known renal or genitourinary structural abnormalities or prior pelvic/GU surgery
- Chronic renal disease
- Patients presenting outside the defined treatment windows

- e. If participants will comprise more than one group or stratification, describe each group (e.g., treatment/intervention, placebo, controls, sham treatment) and provide the number of participants anticipated in each group.

Treatment (2-Scan) Group: N = 24

The group randomized to undergo point-of-care ultrasound to assess bladder fullness, initially and at 30min increments until achieving qualitatively “full” measures by point-of-care ultrasound. When the bladder is determined to be full, the transabdominal pelvic ultrasound will be performed.

Control Group= N= 24

The group randomized to undergo standard practice, which is to place indwelling urethral bladder catheter for purpose of retrograde bladder filling prior to transabdominal pelvic ultrasound.

- f. Indicate which, if any, of the special populations listed below will be involved in the protocol. Include the Special Populations Review Form (SPRF) if indicated.

- Pregnant Women: Attach SPRF—Pregnant Women, Fetuses, Neonates/Nonviable Neonates
- Fetuses: Attach SPRF—Pregnant Women, Fetuses, Neonates/Nonviable Neonates
- Neonates/Nonviable Neonates: SPRF—Pregnant Women, Fetuses, Neonates/Nonviable Neonates
- Prisoners: Attach SPRF—Prisoners
- Minors (<18 years old): Attach SPRF—Minors
- Employees or students at institution where research conducted
- Persons who are temporarily decisionally impaired
- Persons who are permanently decisionally impaired
- Non-English Speakers

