For each box checked, describe why the group is included and the additional protections provided to protect the rights and welfare of these participants who are vulnerable to coercion:

Because Children’s of Alabama routinely treats minors, and because this particular indication is often occurring in minors, we have included minors. Because employees and/or students of UAB or Children’s of Alabama may seek care at Children’s of Alabama, they may be included in the study population, but are not targeted by the study. Potential participants will be informed that their willingness to participate will have no effect on their employment or academic standing with the University/Hospital. Potential participants will also be informed that their willingness to participate will have no impact on the quality of care received.

- g. List any persons other than those directly involved in the protocol who will be at risk. If none, enter “None”: **None**
- h. Describe the recruitment process (e.g., medical record review, referrals, letter of invitation, existing patients) that will be used to seek potential participants (e.g., individuals, records, specimens). Research recruitment by non-treating physicians/staff may require completion of Partial Waiver of Authorization for Recruitment/Screening.

Study staff will be notified by the bedside nurse or treating physician/nurse practitioner of any patient for whom a transabdominal pelvic ultrasound may be ordered. If the patient appears to be eligible, a member of the study staff will approach the patient to explain the study and obtain informed consent/assent. Other clinicians in the pediatric ED will be made aware of the study so that they can directly refer patients to study staff when appropriate. Study staff will utilize CoA's electronic patient tracking system to obtain information on patient's gender, age, and chief complaint, as well as PMH to determine exclusions, including prior bladder or pelvic surgical procedures, or known pregnancy.

- i. If you will use recruitment materials (e.g., advertisements, flyers, letters) to reach potential participants, attach a copy of each item. If not, identify the source (e.g., IRB Protocol Number for approved databases) from which you will recruit participants. Not Used
- j. Describe the screening process/procedures for potential participants. No additional screening procedures are planned.

17. Protocol Procedures, Methods, and Duration - in nontechnical, lay language

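### Does an enrolment window set on ED arrival up to 2300, but justified by sonographer cover for a later scan, need to be changed?

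*Protocol*

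**What the plan says.** Item 16.c describes a convenience sample of patients for whom the treating clinician expects to order a transabdominal pelvic ultrasound and whose "arrival to the ED is between the hours of 0700-2300 on Mondays-Fridays, as this correlates with the times that sonographers are in-house". The same sentence draws the consequence that "real-time attainment, of transabdominal pelvic ultrasounds is achievable".

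The exclusion list in Item 16.d has a matching entry: "Patients presenting outside the defined treatment windows". The only hours defined anywhere are these arrival hours.

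Enrolment comes before the order is certain. The inclusion criterion in Item 16.d is "Likely to have order placed for transabdominal pelvic ultrasound/ovarian ultrasound", and under Item 16.h, once a patient appears eligible, "a member of the study staff will approach the patient to explain the study and obtain informed consent/assent". No last hour is given for this.

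In the intervention arm, Item 17.a says of the bedside bladder scan: "This ultrasound will be obtained immediately upon enrollment and serially at 30-minute intervals until the bladder is determined to be full". Item 17.e caps these scans at five. In the control arm, Item 17.a leaves catheterisation and the timing of imaging to the treating team.

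The primary outcome (Item 14.b) is "time from transabdominal pelvic ultrasound order placed to time of transabdominal pelvic ultrasound image completion". The recorded items in Item 17.a include "Time of order of transabdominal pelvic ultrasound" and the completion time stamped on the radiology report, with the visit date. No randomisation time is listed.

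**The concern.** The limit and its justification refer to different moments. A sonographer is needed at the scan, but the rule tests the time at the door. Several steps lie between the two, and the protocol sets no latest time for the order, the randomisation or the scan.

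If in-house cover ended at about 2300, a patient arriving at 2255 would satisfy the rule and defeat its purpose, whichever arm she was allocated to. A wait for a sonographer after the order would count as minutes in the primary outcome, in a comparison with only 24 patients per arm. Preventing such waits appears to be why the window exists. Without a recorded randomisation time, late enrolments also look hard to pick out afterwards.

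**Working it through.** The protocol gives no figure for this point, so there is nothing to reproduce. Only two inputs come from the document: the arrival window (0700 to 2300, 16 h = 960 min) and the sample size (24 + 24 = 48). Everything else is assumed: even arrivals, enrolment of every late arrival, a lag of 30 or 60 min from door to randomisation, a post-order wait w of 30 to 90 min for each late case, and a base SD of 60 min.

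**Share randomised after cover ends.** p = max(0, lag − minutes of cover past 2300)/960.

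- Cover to 2300: 30/960 = 3.125% and 60/960 = 6.25%, or 1.5 and 3 of 48.
- Cover to 2330: 0 and 30/960 = 3.125%, or 0 and 1.5 of 48.
- Cover to midnight: none at either lag.

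**Added variance if cover ends at 2300.** Added variance = w² × p(1 − p), compared with 60² = 3600.

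- Lag 30 min: p(1 − p) = 0.0303. w = 30 gives 27.2 (0.8%); w = 90 gives 245.2 (6.8%).
- Lag 60 min: p(1 − p) = 0.0586. w = 30 gives 52.7 (1.5%); w = 90 gives 474.6 (13.2%).

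As SD components these run from 5.2 to 21.8 min. A variance rise of v is offset by v more patients, so the range is worth 0.4 to 6.3 of 48 patients.

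**Cost of an earlier limit.** Suppose a last-randomisation time leaves 60 min for preparation and scan (assumed). Window lost = (60 + lag)/960, and the increase in recruitment time = 1/(1 − loss) − 1.

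| Lag | Variance rise avoided (w = 30 to 90) | Window lost | Recruitment longer by |
|---|---|---|---|
| 30 min | 0.8% to 6.8% | 90/960 = 9.4% | 10.3% |
| 60 min | 1.5% to 13.2% | 120/960 = 12.5% | 14.3% |

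Both columns can be read as recruitment effort, and at an SD of 60 the cost is the larger in each row.

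**Sensitivity.** The table favours the existing rule in one respect. It counts the gain only from patients randomised after cover, but the cost from everyone inside the allowance. As an upper bound, give all of the latter the full wait:

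- Lag 30 min: p = 0.09375, p(1 − p) = 0.0850, variance rise 76.5/3600 = 2.1% to 688.2/3600 = 19.1%.
- Lag 60 min: p = 0.125, p(1 − p) = 0.1094, variance rise 98.4/3600 = 2.7% to 885.9/3600 = 24.6%.

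Gain then equals cost at a wait of √(0.1034 × 3600/0.0850) ≈ 66 min for the 30 min lag, and √(0.1429 × 3600/0.1094) ≈ 69 min for the 60 min lag. With the narrower count and an SD of 40, the rises are 1.7% to 15.3% (lag 30) and 3.3% to 29.7% (lag 60), so long waits would favour the cut-off. At an SD of 80 they are 0.4% to 3.8% and 0.8% to 7.4%, and the cost is larger throughout. The sign of the net gain therefore depends on quantities the document does not supply.

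**Longest preparation.** Five scans 30 min apart span (5 − 1) × 30 = 120 min. Allowing for that plus an assumed 30 min pelvic scan would lose 150/960 = 15.6% of the window with no lag and 210/960 = 21.9% with a 60 min lag, making recruitment 18.5% to 28.0% longer.

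**The case for a change.** The best case for a change is that eligibility hours belong in the protocol, and no analysis plan can repair a window tied to the wrong event. The shares above also leave out patients randomised shortly before cover ends whose preparation overruns it. With cover to 2300, a door-to-enrolment time of 0 to 90 min and an assumed 30 min for control filling, the affected part of the window is about 3% to 13% for controls. For intervention patients it is 0.5% to 10% if full at the first scan, and 13% to 22% only if every one needed all five scans.

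Part of this stands. The rule and its reason do refer to different times, and a reader cannot tell from the protocol whether cover extends past 2300.

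The step from there to a defect does not stand:

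- Item 16.c says only that arrival hours correlate with in-house hours and that scans are therefore achievable. A site that knows its own rota may have chosen arrival hours for which that is true.
- Arrival is an outer bound. In a convenience sample, staff can decline to approach a patient when a scan in time is not expected.
- The exclusion is consistent with Item 16.c, since presenting means arriving. Calling the window a treatment window is loose labelling.
- The missing randomisation time matters little. The primary clock starts at the order, and the recorded order and completion times locate any wait inside the outcome once cover hours are known. A wait before the order is outside the outcome.

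**Conclusion.** No change to the plan is called for. The mismatch between rule and reason is real but amounts to missing operational detail. Harm requires three things the protocol does not state: that cover ends at about 2300, that late arrivals are enrolled, and that they wait for a scan after the order.

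If all three hold, 1.5 to 3 of 48 patients are randomised after cover at lags of 30 to 60 min, and variance rises by 0.8% to 13.2% at an SD of 60 min. If cover runs to midnight, none are randomised after cover at those lags. The limit applies before randomisation and equally to both arms, and no direction of bias can be shown: serial scanning may run longer than catheter filling, or a patient may be full at the first scan and be ready sooner.

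Moving the limit would lengthen recruitment by about 10% to 14% for a gain that is smaller under the central assumptions and larger only with long waits or a small SD. Keeping the simple arrival window is a fair trade-off. A sentence giving the actual hours of sonographer cover would settle the question, but the design and analysis do not depend on it.

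### Section 17.a labels a point estimate of kappa 0.6 as excellent, although that value leaves a noticeable share of bedside full readings unconfirmed and 24 scanned patients cannot estimate kappa closely

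*Protocol*

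**What the plan says.** Under section 17.a, a trained study member in the intervention group "will perform a point-of-care bladder ultrasound for qualitative assessment of bladder fullness". The scan is done at enrollment and then "serially at 30-minute intervals until the bladder is determined to be full". The patient's own sensation of fullness can also end the sequence. Stored images are re-read by blinded, ultrasound-qualified physicians "to determine inter-rater reliability of the bedside ultrasound interpretation as well as for quality assurance". The next statement on the result is the rule itself: "A kappa of 0.6 to be considered excellent correlation".

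Three other places bear on it:

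- Section 15 (Background) makes reader reliability a hypothesis: "Our study hypothesizes that similarly reliable results will be able to be obtained by CRNPs currently working in our pediatric ED". It adds that this staff group has not been studied for this task.
- Section 16.e gives the scanned arm as "Treatment (2-Scan) Group: N = 24".
- The table in section 17.e caps the bladder scans at five per participant.

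No other section qualifies the 0.6 rule, gives a source for it, or says how many images will be read.

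**The concern.** The sentence is a decision rule on a point estimate. If the observed kappa reaches 0.6, the protocol already supplies the verdict, however few images lie behind it and whatever disagreements remain. Two things are missing from such a verdict. One is what 0.6 means for the reading that matters, a bedside call of full. The other is sampling error, in a sample where repeated images come from the same 24 patients. The word correlation is also wrong for kappa, which is chance-corrected agreement.

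At stake is the statement that nurse practitioners read bladder fullness reliably. The blinded re-read is the only measurement of reading reliability that the protocol describes, and section 15 presents this staff group as the new element of the study.

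**Working it through.** The protocol gives no derivation, image count or precision for 0.6, so there is no figure of its own to reproduce.

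**Inputs from the protocol**
- Threshold: kappa 0.6 (17.a).
- Patients scanned: 24, intervention arm only (16.e).
- Scans per patient: 1 to 5 (17.e), so 24 to 24 × 5 = 120 images.
- Scanning stops once the bladder is judged full (17.a).

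**Assumptions, because the documents are silent**
- Two categories, full and not full. The scale is an attachment that is not shown.
- Equal margins: both readers call the same share p full.
- About one bedside full reading per patient, because scanning stops there. Then p is about 1 divided by scans per patient: 50% for two, 33% for three, 20% for five.

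**Step 1: disagreement at kappa 0.6**

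Chance agreement is pe = p² + (1 − p)², so 1 − pe = 2p(1 − p). The discordant share is (1 − 0.6)(1 − pe). Half of it, 0.4p(1 − p), is bedside full with the reviewer saying not full. Divided by p, the unconfirmed share of bedside full readings is 0.4(1 − p).

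| Scans per patient | p | Discordant scans | Bedside full not confirmed |
|---|---|---|---|
| 2 | 0.50 | 0.4 × 0.500 = 20% | 0.4 × 0.50 = 20% |
| 3 | 0.33 | 0.4 × 0.444 = 18% | 0.4 × 0.67 = 27% |
| 5 | 0.20 | 0.4 × 0.320 = 13% | 0.4 × 0.80 = 32% |

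Raw agreement improves down the table while the full call is confirmed less often. Outside these cases, discordance is 7.2% at 10% full. It is 26.7% and 30.0% with three and four equally used categories (0.4 × 2/3 and 0.4 × 3/4).

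**Step 2: precision around an observed 0.6**

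At p = 0.5, agreement is 0.8 and SE = √[0.8 × 0.2 / (n × 0.5²)] = √(0.64/n). The 95% interval is 0.6 ± 1.96 SE, with images treated as independent.

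| Images | SE | 95% interval |
|---|---|---|
| 24 | 0.163 | 0.28–0.92 |
| 48 | 0.115 | 0.37–0.83 |
| 72 | 0.094 | 0.42–0.78 |
| 120 | 0.073 | 0.46–0.74 |

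The share full and the image count are linked by the stopping rule, so 50% full does not fit every row. With the large-sample SE for unequal shares, 72 images at 30% full give 0.40–0.80 and 120 images at 20% full give 0.42–0.78. The pairings that fit the design are therefore slightly less precise than the 50% rows.

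**Step 3: clustering**

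Intervals widen by √[1 + (m − 1)ρ] for m images per patient. With m = 3 and an assumed ρ of 0.1, 0.3 or 0.5, the factor is √1.2 = 1.10, √1.6 = 1.26 or √2.0 = 1.41.

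**Step 4: how often the label would be earned by chance**

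This was simulated at 50% full with independent images. If true kappa is 0.5, an observed value of at least 0.6 occurs in 25% of studies with 24 images, 20% with 48 and 10% with 120. If true kappa is 0.4, the figures are 11%, 6% and 1%.

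**The case against.** The strongest reply is that little hangs on this number. Section 14.b lists time to completed ultrasound as primary, and catheterization and pain as secondary; kappa is not among them. The image review also serves quality assurance, and no patient decision or success criterion depends on 0.6. This stands, and it limits the weight of the point.

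Section 17 is meant to be in lay language and itself speaks of inter-rater reliability, so the word correlation is a small slip. The interval method, the handling of repeated images and the reporting of raw agreement could all sit in a statistical analysis plan that is not at hand. This also stands, but the label is fixed in the protocol, and an interval added elsewhere would not remove it.

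Stronger readings are tempting, and the documents do not support them:

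- **That one scan in five is misread.** The 20% needs two categories with half the scans full, neither of which is stated. Kappa also counts disagreement between two readers; it does not show which of them is wrong.
- **That about a third of not-full bladders are called full.** With equal margins that share is 0.4p, which reaches 32% only at p = 0.80, or about 1/0.80 = 1.25 scans per patient. With two, three and five scans it is about 20%, 13% and 8%. The quantity that stays substantial under this design is the unconfirmed share of full calls.
- **That a bedside full reading alone sends the patient to imaging.** Section 17.a also accepts the patient's sensation of fullness.

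**Conclusion.** The point holds, as a minor-to-moderate one. The protocol commits to calling kappa 0.6 excellent. On two categories and equal margins, that value leaves 13% to 20% of scans discordant and 20% to 32% of bedside full readings unconfirmed, over two to five scans per patient. Across the possible 24 to 120 images, the lower 95% limit at 50% full lies between about 0.28 and 0.46 before any allowance for clustering. The label can therefore be attached when the data do not support it.

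The sizes rest on the assumed category count, the equal margins and roughly one full reading per patient. The imprecision is present at every image count the design allows. A reader might infer that the trial's main comparison is compromised, but it is not: the time, catheterization and pain results do not use kappa. Nor do the documents support a particular replacement bar. Requiring the lower limit to reach 0.6 would need an observed kappa of about 0.83 with 24 images or 0.73 with 120 (50% full, independent images), and the protocol shows no sizing for that.

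**What to change.** Delete the sentence that calls kappa 0.6 excellent. In its place, state that:

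- agreement between bedside and blinded readings will be reported as kappa with a 95% confidence interval obtained by resampling patients rather than images;
- raw agreement will be given beside it, with the share of bedside full readings that the blinded reviewer does not confirm;
- any statement about nurse-practitioner reliability will rest on that interval, and not on whether the point estimate passes 0.6.

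No specific lower-limit threshold needs to be set. The images are already to be stored and re-read, so the cost is a short change of wording and a small extra analysis. The price is a reliability statement that will probably read less favourably.
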